2.3 Secondary Endpoints

- Plasma levels of 3HHB and metabolites 3-hydroxybutyrate and 1,3-butanediol over time during (6 hour period) and after the intervention (12 hour period)
- Urine levels of 3HHB and metabolites 3-hydroxybutyrate and 1,3-butanediol over time during (6 hour period) and after the intervention (12 hour period)
- Plasma levels of cholesterol (HDL, LDL, total), triglycerides en free fatty acids over time during (6 hour period) and after the intervention (12 hour period)
- Blood glucose concentrations during the 48h-study period
- Incidence of severe (<40 mg/dl) hypoglycemia during the intervention window and until 12h after stopping study infusion (3HHB or placebo)
- Incidence of ketoacidosis during the intervention window and until 12h after stopping study infusion
- Intolerance for the supplement (including abdominal discomfort or vomiting)

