2.4 Trial Design

This will be a single center trial, in adult critically ill patients. With a cross-over design (Fig. 1), patients will receive in random order on 2 consecutive days 3HHB and placebo.

Patients will receive the investigational product between ICU day 4 and 14, to avoid the time of increase in endogenous ketogenesis that we have previously documented to be present in the first 2 to 3 days in ICU [6]. The investigational product (3HHB) or placebo will be delivered through the enteral feeding tube.

Figure 1: Cross-over design of the trial. In group 1, participants will receive 3HHB on intervention day 1, followed by a placebo on intervention day 2. Group 2 will receive placebo on intervention day 1 and 3HHB on intervention day 2. Repetitive blood sampling is indicated in red.

Patients are typically started on enteral nutrition (EN) within 48 hours of admission, unless they are able to eat. EN is delivered for 2x10h per day (8am-6pm and 8pm-6am), with 2x2h interruption (6-8am and 6-8pm) to measure gastric residual volume (Fig 2). EN is usually started at a low rate, and increased depending on tolerance (as deducted in part from gastric residual volumes). For this trial, the caloric intake will be kept constant over the 2 intervention days avoiding the influence of caloric intake on outcome measures. Patients with nasogastric tubes who are not receiving enteral nutrition are also eligible for inclusion. This will allow to study ketone absorption and clearance in both fed and unfed state in the critically ill patient.

Figure 2: 10 hour feeding scheme. Intermittent administration of 3HHB/placebo (in green) every hour for 6 times.

We will administer 3HHB or placebo via repeated small boluses through the nasogastric feeding tube, as is also done for enterally administered medication. The nasogastric tube will be flushed with a 5% glucose solution prior and after administration of 3HBB or placebo to ensure that the bolus has completely entered the stomach while also avoiding clotting of the nasogastric tube.

The first bolus wil be given at 10 am (after 2 hours of enteral feeding) and this wil be repeated 5 times with one hour interval (6 doses in total). After the last bolus, the patient will be fed for three more hours. The next day, this procedure will be repeated (Fig. 1).

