2.5 Translational research

Blood glucose and 3-hydroxybutyrate concentrations will be quantified repeatedly using blood gas analysis and point-of-care devices during the 48h trial window.

For this trial, we will collect blood samples at 10 ± 1 am on ICU test day I, before administration of the first bolus, repeat this every hour, up to I hour after the last bolus (4 pm), and then every 2 hours until 12h post final bolus (4 am on ICU test day 2). We will repeat this on test day 2. In total, 26 samples (104 ml blood) will be collected from each patient. To minimize blood waste and reduce infection, we will use a VAMP system for blood sampling. Each sample consists of I EDTA tube (purple K2E tube - BD Vactutainer 368861) containing 4 ml of blood. Samples will be stored on ice immediately and processed for further analysis. After processing, samples will be frozen at -20°C and stored at -80°C.

We will collect a urine sample from the 24h urine collection at 8 am ± 1 hours at the end of both intervention days. These samples will be processed, frozen and stored at -80°C for further analysis.

As a standard of care, whole blood glucose measurements are performed every 4 hours on arterial blood using a blood gas analyzer in the ICU. Using the left-over of this clinically collected sample, we will also measure 3-hydroxybutyrate using ketone test strips (Nova StatStrip).

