As described in chapter 2.4 (Trial design), 3HHB and placebo will be administered through the same feeding tube as EN. A syringe with the intervention product will be attached to the tube port and instilled by slowly and steadily pushing on the plunger. A flush of 10 ml 5% glucose will be given after each administration to prevent clotting of the tube. After the last (6th) bolus administration, we will flush with 50 ml 5% glucose. We will also use 5% glucose as placebo.

6 Safety reporting

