7.2 Statistical Analysis

For each patient, and for each study day, maximum concentration, time to reach maximum concentration, delta Max (difference between maxium concentration and baseline concentration), area under the curve, elimination rate and elimination half life will be calculated for 3HBB and its metabolites 3-hydroxybutyrate and 1,3-butanediol. Delta Max of 3-hydroxybutyrate and time within range (plasma 3-hydroxybutyrate 0.22mmol/l above baseline value) will be calculated as primary outcome variables. For blood lipid parameters, maximum concentration, time to reach maximum concentration, delta Max (difference between maximum concentration and baseline concentration), and area under the curve will be calculated. Data will be compared with paired t-tests after transforming the data to near-normally distributed values if needed. If the latter is not possible, non-parametrical tests will be used. Within the crossover design, each patient thus serves as his/her own control.

To investigate whether the order of administration of placebo and 3HHB affected the response, the delta Max of the placebo day and the 3HHB day will be assessed with a repeated measures ANOVA in which the grouping variable will be randomization (placebo/3HHB or 3HHB/placebo) and time is the difference between test day I and test day 2.If more than one dose will be tested, parameters will also be compared between doses. These data will be compared with standard t-tests after transforming the data to near-normally distributed values if needed. If the latter is not possible, non-parametrical tests will be used. P-values will be considered significant when at or below 0.05 without correction for multiple testing. If a higher dose reached a significant increase in the paired analysis, and also compared to the lower dose, this will further strengthen the conclusion that the lower dose was ineffective while the higher dose was effective. If the higher dose does not reach a statistical difference from the lower dose this might suggest that the lower dose already created a small, but non-statistical increase which was not picked-up in the paired analysis.

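### Section 7.2 calls for elimination rate and half-life on the placebo day, and for a paired test against placebo, although nothing is dosed that day

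*Protocol*

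**What the plan says.** Section 7.2 opens its parameter list with "For each patient, and for each study day, maximum concentration, time to reach maximum concentration, delta Max" and continues with "area under the curve, elimination rate and elimination half life will be calculated for 3HBB and its metabolites 3-hydroxybutyrate and 1,3-butanediol". The lipid list that follows has no elimination parameters, so the lists were drawn up analyte by analyte and the ketone list is a deliberate instruction.

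The comparison rule is general: "Data will be compared with paired t-tests after transforming the data to near-normally distributed values if needed", with a non-parametric test as fallback. No parameter is exempted, and the section adds that each patient acts as his or her own control. If more than one dose is tested, parameters are also compared between doses.

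One of the two study days is a placebo day: "patients will receive in random order on 2 consecutive days 3HHB and placebo" (section 2.4). Section 5 gives its content: "We will also use 5% glucose as placebo".

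Two variables are defined relative to baseline, and they are the primary ones: "Delta Max of 3-hydroxybutyrate and time within range (plasma 3-hydroxybutyrate 0.22mmol/l above baseline value) will be calculated as primary outcome variables". For the elimination parameters, section 7.2 mentions no baseline correction.

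**The concern.** An elimination rate describes the disappearance of something that was given. On the placebo day no ester is given, so no butanediol is formed from it. The elimination rate, half-life and time to maximum of these two analytes then have no meaning. 3-hydroxybutyrate is present, but only as the endogenous level. The slope of its logarithm is drift plus assay noise, and half-life is ln 2 divided by that slope, which is unstable when the slope is near zero and undefined when it is not negative. Neither a transformation nor a rank test can repair a pair whose placebo member is missing or meaningless. Section 7.2 also declines to impute missing data.

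The 3HHB day raises a second, milder problem. Measured 3-hydroxybutyrate is the endogenous level plus the administered part. If the endogenous part is left in, the log-concentration curve flattens onto it and the fitted half-life is too long. The distortion is larger when the rise is small, so it would also enter the comparison between doses. Section 2.4 gives ketone absorption and clearance as a reason for including both fed and unfed patients, and section 1 reports slower clearance in septic mice than in healthy mice. A half-life from this trial would therefore be read with interest.

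**Working it through.** **Inputs from the protocol.** Section 2.5 samples hourly from 10 am to 4 pm (7 samples), "and then every 2 hours until 12h post final bolus (4 am on ICU test day 2" (6 more). That is 13 per day and 2 × 13 = 26 in all, which matches the stated total. The last bolus is at 3 pm, so seven samples (4, 6, 8, 10 pm, midnight, 2 and 4 am) are available for a terminal slope. Sixteen completers are planned per dose. The protocol states no half-life, elimination rate or endogenous concentration, so there is no figure of its own to reproduce on this point.

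**Assumptions.** All concentrations, half-lives and noise levels below are assumed. Carry-over is ignored.

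**Step 1, placebo day.** Take a flat endogenous level with independent sample-to-sample variation of SD s on the log scale. Fit ln c against time by least squares, with t = 0, 2, ..., 12 h.

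- Σ(t − 6)² = 36 + 16 + 4 + 0 + 4 + 16 + 36 = 112, so the slope has mean 0 and SD s/√112.
- A slope centred on zero is zero or positive with probability 0.5. In simulation the share was 50% for s = 0.1, 0.2 and 0.3. On those days no half-life exists.
- Among the remaining days the median half-life is ln 2 ÷ (0.674 × s/√112). This is about 109 h for s = 0.1, 54 h for s = 0.2 and 36 h for s = 0.3. The result is set by the noise alone.
- The chance that all 16 patients give a placebo half-life is 0.5¹⁶ ≈ 0.000015. On average about 8 of 16 pairs would be lost, and chance would decide which.

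The maximum does not fail in this way. Under the same flat profile at 0.1 mM, the mean placebo delta Max of 3-hydroxybutyrate is about 0.02 to 0.06 mM, a small and perfectly usable control value.

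**Step 2, 3HHB day.** Let c(t) = B + A·exp(−kt), with t counted from 4 pm, B the endogenous level, A the administered part at 4 pm, and k = ln 2 / 2 h.

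Worked case with B = 0.10 and A = 0.22 mM: c = 0.320, 0.210, 0.155, 0.1275, 0.1138, 0.1069, 0.1034. Then Σ(t − 6)·ln c = −10.097, the slope is −10.097/112 = −0.0901 per hour, and the half-life is 0.693/0.0901 = 7.7 h against a true 2 h.

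| B (mM) | A (mM) | all seven samples | first three |
|---|---|---|---|
| 0.05 | 0.22 | 5.2 h | 2.9 h |
| 0.10 | 0.22 | 7.7 h | 3.8 h |
| 0.20 | 0.22 | 12.3 h | 5.6 h |
| 0.05 | 2.0 | 2.5 h | 2.1 h |
| 0.10 | 2.0 | 3.0 h | 2.2 h |
| 0.20 | 2.0 | 3.7 h | 2.4 h |

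Every value lies above 2 h, so the direction is fixed. The size runs from slight to about sixfold. Subtracting B returns exactly 2 h, by construction of the model.

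**Step 3, between doses.** Keep the true half-life at 2 h and B = 0.10 mM, and let the rise grow in proportion to dose: 0.22, 0.44 and 0.66 mM. The seven-sample fit gives 7.7, 5.2 and 4.3 h. The higher doses would appear to clear faster when clearance is in fact the same.

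**The case against.** There are four objections of substance.

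- **The crossover supplies a valid control for most parameters.** This stands. A reader might infer that every parameter in the list fails on the placebo day. It does not. The placebo-day maximum, delta Max, time within range and AUC of 3-hydroxybutyrate are well defined and are what the design exists to provide. For AUC, the paired placebo day already accounts for the endogenous contribution. For the ester and 1,3-butanediol the placebo maximum is simply near zero.
- **The fitting window, baseline handling and rules for inestimable values belong in the SAP, which is not shown.** This stands too. Their absence is no error in itself, and the protocol does not say that uncorrected values will be fitted. The order to compute elimination on each study day and to test it in pairs is different, because the protocol itself states it.
- **The size of the 3HHB-day bias comes from assumed inputs.** This is correct. A reader might infer from the 7.7 h case that half-lives will be grossly inflated. The documents do not support that: with a rise of 2.0 mM and the first three samples, the fit gives 2.1 to 2.4 h. Section 2.4 also places dosing after the early endogenous rise. Only the direction is certain.
- **Half-life is not a named endpoint.** Section 2.3 lists "Plasma levels of 3HHB and metabolites 3-hydroxybutyrate and 1,3-butanediol over time during (6 hour period) and after the intervention (12 hour period"), which concerns levels, not elimination. This limits the importance of the point but does not make the instruction workable.

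**Conclusion.** The concern holds for a limited set of parameters: elimination rate and half-life of all three analytes, and time to maximum of the ester and 1,3-butanediol. On the placebo day these do not exist for the ester and butanediol, and are noise for 3-hydroxybutyrate. The paired test on them is invalid. This follows from the protocol's own text. The figure of about half of placebo days without a positive half-life rests on an assumed flat endogenous profile.

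The upward bias of an uncorrected 3-hydroxybutyrate half-life on the 3HHB day is certain in direction, given a stable endogenous level, but its size is unknown. It depends on endogenous level, rise and fitting window, none of which the protocol gives. Because the bias shrinks as the rise grows, it would also distort the comparison between doses.

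A reader might infer that the trial's main conclusion is at risk. It is not. Delta Max and time within range are referenced to baseline, the escalation rule in section 7.1 rests on the increase in 3-hydroxybutyrate, and the sample size of 16 does not involve elimination. Only secondary pharmacokinetic descriptors are affected. The point is still worth correcting, because the rule as written cannot give a valid result and the remedy is cheap.

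**What to change.** In section 7.2:

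- Estimate elimination rate and half-life (all three analytes), and time to maximum of the ester and 1,3-butanediol, on the 3HHB day only. Summarise them descriptively, with no paired test against placebo.
- State that 3-hydroxybutyrate elimination is computed on baseline-corrected values, so that any comparison between doses is not driven by the size of the rise. The fitting window and the rule for inestimable values can go in the SAP.
- Keep the paired 3HHB-versus-placebo comparisons of 3-hydroxybutyrate maximum, delta Max, time within range and AUC as planned. Name them explicitly, so that the restriction cannot be read as removing a primary variable from its test.

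The cost is wording and analysis code, with no extra samples or patients. The downside is that some patients may have no estimable half-life, and the number should be reported.

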7.1 Sample Size

The study is powered to detect a 0.22 mM within-patient increase in plasma 3HB with 95% certainty, 80% power, calculated with a paired t-test. The anticipated effect size is 0.786 given that patients not treated with ketone esters have a mean difference of 0.001mM between intervention day I and 2 with a SD of 0.28mM (based on prior data from ICU patients) and the anticipated required increase with the administration of ketone esters is 0.22mM (which was the effective increase in the mice studies). If the lower limit of the 95% confidence interval is not above 0.22mM increase, a higher dose will be tested.

Approximately 160 participants will be screened to achieve 16 participants completing the 48h study period or an estimated total of 8 evaluable participants per treatment group.

The screening will be repeated for each dose study. In total a maximum of approximately 480 patients will be screened and a maximum of 3x 16 patients completing the 48h study period will be included.

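### The planned lipid summaries are built for a rise: a lipid that falls during dosing and recovers before 4 am leaves maximum and delta Max near baseline; a signed change should be added

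*Protocol*

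**What the plan says.** Protocol section 2.3 lists as a secondary endpoint "Plasma levels of cholesterol (HDL, LDL, total), triglycerides en free fatty acids over time during (6 hour period) and after the intervention (12 hour period"). It names the dosing and post-dosing periods separately and gives no expected direction.

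Section 7.2 fixes how lipids are summarised: "For blood lipid parameters, maximum concentration, time to reach maximum concentration, delta Max (difference between maximum concentration and baseline concentration"). The fourth summary closes the same sentence: "and area under the curve will be calculated". This is the list used for the ester and its metabolites without the elimination terms. It contains no minimum and no signed change over a set period. It does not say whether the pre-dose sample counts towards the maximum, over what window AUC is taken, or whether AUC is baseline-corrected.

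The comparison is between the 3HHB day and the placebo day: "Data will be compared with paired t-tests after transforming the data to near-normally distributed values if needed".

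Section 2.5 sets the sampling. Blood is drawn at 10 am "before administration of the first bolus, repeat this every hour, up to I hour after the last bolus (4 pm"). Sampling thins out after that, with the rest of the schedule given as "and then every 2 hours until 12h post final bolus (4 am on ICU test day 2").

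**The concern.** Maximum, time to maximum and delta Max suit a compound that is given, rises from baseline and clears. Lipids are not given and may move either way. Of the four summaries, delta Max is the only one defined as a change from baseline, and it looks only at the highest value of the day. A lipid that drops during dosing and returns to its starting level before sampling ends has its highest value before or after the drop, so the depth of the drop does not enter delta Max.

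What is at stake is the reading of one secondary endpoint. A recovering fall could be reported as little or no change in the named change-from-baseline measure, leaving AUC to carry the finding alone.

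**Working it through.** **1. The plan's own figure.** Section 7.1 sizes the trial "with 95% certainty, 80% power, calculated with a paired t-test". The effect size is 0.22/0.28 = 0.786. Exact two-sided paired t-test power at alpha 0.05 is 0.776 for n = 14, 0.808 for n = 15 and 0.836 for n = 16, so 16 completers per dose is adequate. This concerns 3-hydroxybutyrate; no effect or variability is given for lipids.

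**2. Sampling grid.** Hourly from 10 am to 4 pm is 7 samples; two-hourly from 6 pm to 4 am is 6. That is 13 a day and 26 over two days, matching "In total, 26 samples (104 ml blood) will be collected from each patient". The span is 18 h.

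**3. Example without noise.** A lipid is 0.6 at 10 am, 0.2 from 11 am to 4 pm, 0.4 at 6 pm and 0.6 from 8 pm on.

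| Summary | Recovering fall | Flat at 0.6 |
|---|---|---|
| Maximum | 0.6 | 0.6 |
| Delta Max | 0.0 | 0.0 |
| AUC (trapezoid) | 0.4 + 1.0 + 0.6 + 1.0 + 4.8 = 7.8 | 0.6 × 18 = 10.8 |

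Two-thirds of the level is lost for five hours, and delta Max is the same as for a patient who never moved.

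**4. Paired comparison, recovering fall.** Assumptions, none from the documents: the shape in step 3, independent sample error with within-day SD 1, n = 16, two-sided 0.05. Simulated 3HHB-minus-placebo shift in delta Max, in SD units:

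| True fall | Pre-dose not counted | Pre-dose counted |
|---|---|---|
| 1 | -0.35 | -0.32 |
| 2 | -0.44 | -0.39 |
| 4 | -0.47 | -0.40 |
| 8 | -0.47 | -0.40 |

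Power is 12 to 19% throughout. The plateau can be checked by hand. Once the fall is deep, the maximum comes only from the five samples from 8 pm to 4 am instead of all twelve post-dose samples. The expected maxima of 5 and 12 standard normal values are 1.163 and 1.629, a difference of -0.47. With the pre-dose sample counted they are 1.267 (6 values) and 1.668 (13 values), a difference of -0.40.

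**5. A signed change on the same data.** Take the mean of the six samples from 11 am to 4 pm minus the pre-dose value. Its variance per day is 1 + 1/6, so the SD of the paired difference is √(2 × 1.167) = 1.53. A 1 SD fall has effect size 1/1.53 = 0.65 and power 69%; from 2 SD power exceeds 99%. A shift in a day's overall level cancels.

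**6. AUC over the full 18 h.** The trapezoid weights sum to 18 and their squares to 28.5. A 1 SD fall changes AUC by (10.8 - 7.8)/0.4 = 7.5.
- No day-to-day level shift: SD of the difference √(2 × 28.5) = 7.55, effect size 0.99, power 96%.
- Day-level SD 1 (assumed): √(2 × (28.5 + 324)) = 26.6, effect size 0.28, power about 19%; for a 2 SD fall, 0.56 and 56%.
- Subtracting the single pre-dose value over 18 h barely helps: about 20% and 58%.

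**7. Fall lasting to 4 am.** With full depth from 11 am to 4 am, paired delta Max has 61 to 64% power at 1 SD and at least 99% at 2 SD. If the pre-dose sample counts, the shift stops at -1.67 SD even for an 8 SD fall, because the pre-dose value itself becomes the maximum.

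**8. Second set of assumptions.** Percentage falls, between-day log SD 0.15, between-patient log SD 0.4, within-day CV 10% or 20%, pre-dose counted. A transient 40% fall, back at baseline by 12 h, gives these powers:

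| Summary | CV 10% | CV 20% |
|---|---|---|
| Delta Max | 0.25 | 0.22 |
| AUC | 0.83 | 0.79 |
| Minimum minus baseline (delta Min) | 1.00 | 0.73 |

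For sustained falls of 20/40/60% at CV 10%, delta Max has power 0.98/1.00/1.00, but its shift is -0.163/-0.193/-0.195 of baseline, so it again does not track depth. For a sustained 20% fall at CV 20%, delta Max (0.71) does better than delta Min (0.33).

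**The case against.** A reader might infer that the peak-based summaries cannot measure a fall at all, that a drop of any size is scored as zero, or that the lipid endpoint answers only half its question. The documents do not support this:

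- The test is paired against the placebo day. A fall lasting to 4 am removes high values that the placebo day still has, so maximum and delta Max drop and delta Max detects it well (steps 7 and 8). Even for a recovering fall the paired shift is small, not zero.
- AUC is planned in the same sentence and responds to falls of either shape.
- The low AUC power in step 6 needs an 18 h window and a day-to-day SD as large as the within-day SD. Section 7.2 states no window, section 2.3 names two periods, and an AUC per period would be compatible with both. That detail may sit in a statistical analysis plan not seen here.
- Nothing in the protocol predicts a fall in any lipid. The one lipid mechanism in section 1 is conversion of 3-hydroxybutyrate to cholesterol.
- Lipids are a secondary endpoint, are absent from the synopsis list, have no power target and do not enter the escalation rule.

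All of this stands and limits the point to falls that recover within the sampling window. It does not remove it. Section 7.2 itself fixes the list of lipid summaries, and the single change-from-baseline measure in it misses such a fall whether or not the pre-dose sample counts. No prediction of a fall is needed: an endpoint without a stated direction should be measurable in both.

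**Conclusion.** The point holds in limited form and is minor. For a lipid that falls during dosing and recovers before 4 am, the insensitivity of maximum and delta Max follows from their definitions and needs no variability assumption. The size of the loss in the paired test does: with the assumed shape and SD, the delta Max shift levels off at -0.40 to -0.47 SD with 12 to 19% power, against 69% (1 SD) and over 99% (2 SD) for a mean signed change over the dosing samples.

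For a fall that persists to 4 am the concern is about size, not detection: its depth is understated if the pre-dose sample counts towards the maximum. AUC covers both shapes; its reduced sensitivity to a fall confined to dosing is conditional on the window and on day-to-day variability that the documents do not give. No decision on the primary endpoint, sample size or dose escalation is affected.

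**What to change.** In section 7.2, keep the four planned lipid summaries and add a signed change from that day's pre-dose value: the mean over the dosing samples (11 am to 4 pm) and, separately, over the post-dosing samples (6 pm to 4 am). Compare the 3HHB and placebo days two-sided. This also carries the two periods named in section 2.3 into the analysis. Minimum and delta Min would serve as an alternative. Removing the peak summaries is unnecessary, since they remain informative for rises and for lasting falls. It would help to state at the same time whether the pre-dose sample counts towards the maximum.

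The cost is one or two sentences and a simple derivation from samples already drawn. The downside is more secondary comparisons at an uncorrected 0.05: five lipids times two periods is ten per dose, on top of the planned five times four, so they should be read as descriptive.

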Preclinical research by our group further strengthens the **potential clinical benefit of increasing plasma 3-hydroxybutyrate in critically ill patients**. Indeed, in a mouse model of sepsis-induced prolonged critical illness, we demonstrated that exogenous administration of the ketone body 3-hydroxybutyrate, administered as daily bolus injections of a racemic mixture of R,S-3-hydroxybutyrate sodium salt (3HB-Na), significantly attenuated the development of muscle weakness [7]. Subsequent dose-response and toxicity studies revealed that ketone esters are preferred to ketone salts, with a broader therapeutic window [8]. Indeed, the effective dose of 5g/kg/day of the ketone salt 3HB-Na was close to the toxic threshold [9], whereby increased morbidity and mortality by increased doses are likely explained by excessive sodium intake, since ketone esters have a substantially higher threshold for toxicity.

A potentially **safer alternative** for ketone salts is the ketone ester R-3-hydroxybutyl-R-3hydroxybutanoate (**3HHB**) which is endogenously converted to two 3-hydroxybutyrate molecules [10]. The ketone ester is hydrolyzed to 3-hydroxybutyrate and 1,3-butanediol by esterases that are located in the circulation, in the gastro-intestinal tract, the liver, and other tissues [11]. The butanediol molecule is further metabolized to 3-hydroxybutyrate in the liver by alcohol and aldehyde dehydrogenases [11, 12]. We demonstrated that treatment of septic mice with the ketone ester 3HHB **improved muscle weakness** from a dose of 3.5 g/kg/day onward [13]. Up to a dose of 7 g/kg/day 3HHB, signs of organ damage or liver toxicity were absent. However, septic mice showed a higher peak plasma concentration and slower 3-hydroxybutyrate clearance than healthy control mice, leading to toxicity with a bolus of 14 g/kg/day. **This toxicity of a single bolus was completely avoided by a continuous intravenous infusion of this dose** (i.e. 14 g/kg/day) over 24h, while the protective effect on muscle weakness remained equally present [13]. This preclinical research has led to a patent application PCT/EP2017/081394 which is currently in its national phase.

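### The primary paired t-test leaves out the test-day (period) effect of the crossover, and the order ANOVA does not say which of its terms means order

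*Protocol*

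**What the plan says.** Section 2.4 randomises patients to the order of 3HHB and placebo on two consecutive days. Section 4.3 uses blocks of 4, and section 7.1 expects about 8 evaluable patients per sequence out of 16. Section 2.4 replaces patients who do not complete for reasons unrelated to the safety of the intervention, and section 7.2 makes the completers the primary analysis set.

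For the analysis, section 7.2 names delta Max of 3-hydroxybutyrate (maximum minus baseline, per patient and day) and time in range as primary outcome variables, and states: "Data will be compared with paired t-tests". Neither period nor sequence appears. A separate repeated measures ANOVA of delta Max is meant to show whether order mattered; in it "the grouping variable will be randomization (placebo/3HHB or 3HHB/placebo) and time is the difference between test day I and test day 2". The protocol does not say which term answers the question or what follows from a significant result.

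Section 7.1 says that the study is "powered to detect a 0.22 mM within-patient increase in plasma 3HB with 95% certainty, 80% power, calculated with a paired t-test", citing for untreated patients a "mean difference of 0.001mM between intervention day I and 2 with a SD of 0.28mM". It then makes the step to a higher dose depend on whether the lower 95% limit lies above 0.22 mM.

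**The concern.** In a two-period, two-sequence crossover, the difference between a patient's 3HHB and placebo days contains the treatment effect plus or minus any difference between test days. A paired t-test treats that day difference as noise. If the sequences end with unequal numbers, part of it also enters the estimate. The interval from this analysis decides whether a higher dose is tested, so width and bias both matter.

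The order ANOVA raises a second problem. With sequence as group and test day as time, a working dose shows up as a group-by-time interaction. Someone looking for an order effect could take that term for one. The term that does bear on carry-over rests on 8 against 8 patients, so a non-significant result would say little.

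Carry-over is worth a proper check. The last day-1 bolus falls at 3 pm and the day-2 baseline at 10 am, 19 hours later. The background section reports "slower 3-hydroxybutyrate clearance than healthy control mice" in septic mice. Delta Max on day 2 subtracts that baseline.

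**Working it through.** **Inputs from section 7.1.** Target 0.22 mM; SD of the within-patient day difference 0.28 mM; 16 completers, 8 per sequence; untreated day difference 0.001 mM. The test is taken as two-sided at 0.05, because the decision uses a 95% CI. **Assumed, because the protocol gives no figure:** larger day shifts of 0.10 and 0.20 mM, dropout of 10% and 20%, and between-day correlation of 0 to 0.7. Power below is against zero, as in section 7.1.

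**1. The plan's figure.** Effect size 0.22/0.28 = 0.786, as stated. The paired t-test needs 15 patients (80.8% power); 16 give 83.6%. The planned 16 is reproduced closely.

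**2. What the paired test does with a day shift π (day 2 minus day 1).** With treatment effect τ, the expected 3HHB-minus-placebo difference is τ − π when 3HHB comes first (n1 patients) and τ + π when placebo comes first (n2 patients). The paired mean therefore estimates τ − π(n1 − n2)/16, and the expected sample variance at 8:8 is 0.28² + π²·16/15.

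At 8:8 the estimate is unbiased for every π. Simulated power at τ = 0.22:

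| Shift π (mM) | Paired t-test | Period-adjusted (df 14) |
|---|---|---|
| 0.001 | 83.6% | 83.2% |
| 0.10 | about 80% | 83.2% |
| 0.20 | about 69% | 83.2% |

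The paired test is conservative here: its actual type I error is 3.8% at 0.10 mM and 1.7% at 0.20 mM.

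**3. Interval width.** With no shift the half-width is 2.131 × 0.28/4 = 0.149 mM (df 15). Period-adjusted it is 2.145 × 0.28/4 = 0.150 mM (df 14), whatever the shift. With π = 0.20, the paired SD is √(0.0784 + 0.04 × 16/15) = 0.348, giving 2.131 × 0.348/4 = 0.185 mM.

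**4. Unequal sequences.** At 10:6 the bias is π × 4/16. For π = 0.10 that is 0.025 mM in size, so 0.22 becomes 0.195 or 0.245 depending on direction. In the 0.195 case paired power is about 70%, against 80.8% period-adjusted. At 9:7 the factor is 2/16 = 12.5%. Simulating blocks of 4 with random dropout until 16 complete gives a split of 10:6 or worse in about 4.5% of cohorts at 10% dropout and about 11% at 20%.

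**5. What the ANOVA terms mean.** Day 2 minus day 1 has expectation π − τ with 3HHB first and π + τ with placebo first. The gap between sequences is 2τ, so sequence-by-day is treatment. The average is π, so day is period. Simulation agrees: with τ = 0.22 and nothing else, the interaction rejects in 83% of runs and the other two terms in about 5% each. With a day shift of 0.22 alone, day rejects in 83% and the interaction in about 5%.

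**6. Carry-over test (sequence main effect, 8 against 8).** The SD of the two-day sum is 0.28·√((1+ρ)/(1−ρ)), and the standard error of the difference is that SD × √(2/8). For a carry-over of 0.22 mM:

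| Correlation ρ | SD of sum | Power |
|---|---|---|
| 0 | 0.280 | 31% |
| 0.3 | 0.382 | 19% |
| 0.5 | 0.485 | 14% |
| 0.7 | 0.667 | 9% |

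**7. Residual at the day-2 baseline.** A residual c in the 3HHB-first sequence lowers its placebo-day delta Max by up to c. Averaged over two equal sequences, the treatment effect is inflated by up to c/2. Period adjustment does not remove this.

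**The case against.** The strongest reply is that on the protocol's own figures nothing is lost. With a 0.001 mM day difference and 8:8 completers, the paired test is marginally more powerful than the adjusted one, and its estimate is unbiased. Section 2.4 also holds caloric intake constant over both days, which removes one source of a day effect. All of this stands. It is limited only by the fact that section 7.1 does not say the 0.001 mM refers to delta Max.

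A reader might infer that the primary estimate is biased as planned. The documents do not support that: bias needs both a day shift and unequal sequences, and splits of 10:6 or worse are uncommon. A reader might also infer that the protocol would report a working dose as an order problem. Section 7.2 never says the interaction will be read as order; it leaves the term unnamed, so the misreading is a risk and not a stated rule. The ANOVA as worded is also useful, since it contains a valid period test and the period-adjusted treatment test.

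The carry-over evidence is thin. The mouse finding concerns septic against healthy animals, with toxicity at a bolus of 14 g/kg/day, and says nothing about patients 19 hours after the last of six small boluses. Low power of the sequence test is common to this design, and the 9% to 31% range rests on an assumed correlation. Finally, section 7.2 already compares maximum concentration by day and calculates elimination half-life, so part of what carry-over calls for is planned.

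A separate statistical analysis plan could name the ANOVA terms. The protocol itself, however, fixes a paired test without period and describes the ANOVA incompletely, so the wording is worth correcting there.

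**Conclusion.** The point holds as an inexpensive improvement to the analysis, not as a flaw that invalidates the trial. On the plan's figures the cost of omitting period is practically nil. It becomes material only under assumptions that the protocol neither states nor rules out: a day shift in delta Max of more than about 0.10 mM (power about 80%, falling to 69% at 0.20 mM), or a shift combined with sequences unbalanced by replacement (0.025 mM at 10:6 with a 0.10 mM shift). The ANOVA wording needs correction in any case, because its interaction is the treatment effect and its carry-over term has low power. No residual at the day-2 baseline is demonstrated; the c/2 inflation is a bound on what an unknown c could do.

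**What to change.** In section 7.2:

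- Take the primary estimate and its 95% CI, which feed the dose decision in section 7.1, from a crossover model with treatment, period and sequence as fixed effects and patient as random. For complete pairs this is equivalent to comparing the day differences between the two sequences.
- State that in the repeated measures ANOVA the sequence-by-day term is treatment and the day term is period.
- Do not rely on the sequence main effect to exclude carry-over. Report pre-dose 3-hydroxybutyrate on day 2 minus day 1, by sequence, with a CI; section 2.5 already collects both samples.
- Name the already planned maximum-concentration comparison as the sensitivity analysis for baseline subtraction.

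The cost is one degree of freedom: power 83.2% instead of 83.6%, and a half-width of 0.150 instead of 0.149 mM. The 16 completers per dose stay as they are, and no new samples are needed.
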